## 1.3. Schedule of Activities (SoA)

The schedule of activities table provides an overview of the protocol visits and procedures. Refer to Section 8 of the protocol for detailed information on each assessment required for compliance with the protocol.

The Investigator may schedule visits (unplanned visits) in addition to those listed in the schedule of activities table in order to conduct evaluations or assessments required to protect the well-being of the participant.

## 1.3.1. Screening and Cycle 1

Visit Identifier	Screening*	Cycle 1 (21 days)	Notes  *to be obtained within 28 days prior to registration
Visit Window	≤28 days	Day 1 (±1 day)	(X) refer to specific footnote when the measurement may be optional /repeat measurement might not be required.
Informed consent	X		Must be obtained prior to undergoing any study specific procedures that are not considered standard of care.
Tumor history	X		
Medical history	X		Data on prior anti-cancer therapy will be collected along with the best-known response from the previous ALK inhibitor.
Physical examination	X	X	
Weight	X	X	
Performance Status	X	X	
Contraception check (as appropriate)		X	
Laboratory	·		
Hematology	X	(X)	No need to repeat on C1D1 if baseline assessment performed within 7 days prior to that date. For those visits after C1D1, hematology labs should be performed according to lorlatinib product information.

Visit Identifier	Screening*	Cycle 1 (21 days)	Notes  *to be obtained within 28 days prior to registration
Visit Window	≤28 days	Day 1 (±1 day)	(X) refer to specific footnote when the measurement may be optional /repeat measurement might not be required.
Blood Chemistry	X	(X)	No need to repeat on C1D1 if baseline assessment performed within 7 days prior to that date. For those visits after C1D1, blood chemistry should be performed according to lorlatinib product information.
Pregnancy test	X	(X)	For female participants of childbearing potential, a serum or urine pregnancy test will be performed once at the start of screening and once at the baseline visit, immediately before study intervention administration. The pregnancy test should be performed at the clinical site's local laboratory.
Cardiac Monitoring	 		
12-lead ECG	X	(X)	No need to repeat on C1D1 if baseline assessment performed within 7 days prior to that date. During study treatment additional triplicate ECGs may be performed as clinically indicated and according to lorlatinib product information.

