LVEF Assessment	X		Echocardiogram or MUGA will be performed. During study treatment additional assessments may be performed as clinically indicated and according to lorlatinib product information.
			For France and Germany, a transthoracic echocardiogram (TTE) will be performed every 6 months (± 2 weeks) during treatment, and only at the end of treatment visit if the previous assessment was > 1 month. Pulmonary arterial pressure (PAP) will be assessed.
Registration	·		
Registration		(X)	Registration will be within 2 days prior to study treatment start.
Tumor Assessments			
CT and MRI Scan or Equivalent	X		Tumor assessments will include all known or suspected disease sites. CT or MRI scans of Chest Abdomen Pelvis [CAP] and MRI of the brain will be performed at screening. Bone scans (or bone MRI if preferred by investigator) will be performed at baseline for all participants and repeated every 12 weeks on study only if evidence of bone metastases is observed at baseline.

Visit Identifier	Screening*	Cycle 1 (21 days)	Notes  *to be obtained within 28 days prior to registration	
Visit Window	≤28 days	Day 1 (±1 day)	(X) refer to specific footnote when the measurement may be optional /repeat measurement might not be required.	
Cerebrospinal fluid if leptomeningeal/carcinomatous meningitis [LM/CM] disease is present	X		CSF is mandatory for participants who have asymptomatic radiologically suspected leptomeningeal disease (LM) or carcinomatous meningitis (CM) but negative spinal fluid.	
Other Clinical Assessments	Other Clinical Assessments			
Adverse Events	X	X	For AEs and SAEs, the active reporting period to Pfizer or its designated representative begins from the time that the participant provides informed consent, which is obtained prior to the participant's participation in the study through and including a minimum of 28 calendar days after the last administration of the study intervention. Refer to Section 8.3.1 for all specifications.	
Concomitant medications and non- drug supportive interventions	X	X		

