## **Prior/Concomitant Therapy**

11. Radiation therapy (except palliative to relieve bone pain) within 2 weeks of study entry. Palliative radiation ( $\leq$ 10 fractions) must have been completed at least 48 hours

prior to study entry. Stereotactic or small field brain irradiation must have completed at least 2 weeks prior to study entry. Whole brain radiation must have completed at least 4 weeks prior to study entry.

- 12. Prior irradiation to >25% of the bone marrow.
- 13. Concurrent use of any of the following food or drugs (consult the sponsor if in doubt whether a food or a drug falls into any of the above categories) within 12 days prior to the first dose of lorlatinib:
  - a. Known strong CYP3A inducers (eg, carbamazepine, enzalutamide, mitotane, phenytoin, rifampin, St. John's Wort).
  - b. Known strong CYP3A inhibitors (eg, strong CYP3A4 inhibitors: grapefruit juice or grapefruit/grapefruit related citrus fruits [eg, Seville oranges, pomelos], boceprevir, cobicistat, clarithromycin, conivaptan, diltiazem, idelalisib, indinavir, itraconazole, ketoconazole, lopinavir, nefazodone, nelfinavir, paritaprevir and posaconazole, ritonavir, alone and with danoprevir or elvitegravir or indinavir or lopinavir or paritaprevir or ombitasvir or dasabuvir or saquinavir or tipranavir, telaprevir, troleandomycin, and voriconazole, grapefruit juice or grapefruit/grapefruit related citrus fruits [eg, Seville oranges, pomelos]). The topical use of these medications (if applicable), such as 2% ketoconazole cream, is allowed. Note that strong CYP3A inhibitors can be stopped up to one day prior to first dose of lorlatinib on study.
  - c. Known CYP3A substrates with narrow therapeutic index, such as astemizole\*, terfenadine\*, cisapride\*, pimozide, quinidine, tacrolimus, cyclosporine, sirolimus, alfentanil, fentanyl (including transdermal patch) or ergot alkaloids (ergotamine, dihydroergotamine) (\*withdrawn from United States [US] market).
  - d. Known permeability glycoprotein (P-gp) substrates with a narrow therapeutic index (eg, digoxin).
- 14. Major surgery within 4 weeks prior to enrollment. Minor surgical procedures (eg, port insertion) are not excluded, but sufficient time should have passed for adequate wound healing.

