#### 8. STUDY ASSESSMENTS AND PROCEDURES

- The investigator (or an appropriate delegate at the investigator site) must obtain a signed and dated ICF before performing any study-specific procedures.
- Study procedures and their timing are summarized in the SoA. Protocol waivers or exemptions are not allowed.
- Immediate safety concerns should be discussed with the sponsor immediately upon occurrence or awareness to determine if the participant should continue or discontinue study intervention.
- Adherence to the study design requirements, including those specified in the SoA, is essential and required for study conduct.
- All screening evaluations must be completed and reviewed to confirm that potential participants meet all eligibility criteria. The investigator will maintain a screening log to record details of all participants screened and to confirm eligibility or record reasons for screening failure, as applicable.
- Every effort should be made to ensure that protocol-required tests and procedures are completed as described. However, it is anticipated that from time to time there may be circumstances outside the control of the investigator that may make it unfeasible to perform the test. In these cases, the investigator must take all steps necessary to ensure the safety and well-being of the participant. When a protocol-required test cannot be performed, the investigator will document the reason for the missed test and any corrective and preventive actions that he or she has taken to ensure that required processes are adhered to as soon as possible. The study team must be informed of these incidents in a timely manner.

• Procedures conducted as part of the participant's routine clinical management (eg, blood count) and obtained before signing of the ICF may be utilized for screening or baseline purposes provided the procedures met the protocol-specified criteria and were performed within the time frame defined in the SoA.

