# **Lesions with prior local treatment:**

 Tumor lesions situated in a previously irradiated area, or in an area subjected to other loco-regional therapy, are usually not considered measurable unless there has been demonstrated progression in the lesion.

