5.2.8. Adequate Baseline Tumor Assessment

Adequate baseline is defined using the following criteria:

- All baseline assessments must be within 28 days prior to and including the date of first dose.
- All documented lesions must have non-missing assessments (ie, non missing measurements for target lesions and non missing lesions status at baseline for non-target lesions).
- Measurable disease at baseline (see Section 5.2.5 for the definition of measurable disease)

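### Radiotherapy may fall between the baseline scan and first dose, and no rule stops the resulting shrinkage from counting as response; the effect falls mainly on intracranial response

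*Protocol*

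**What the plan says.** **Radiotherapy before entry (Protocol 5.2, criterion 11).** Radiotherapy other than palliative treatment of bone pain is excluded within 2 weeks of entry. For the brain: "Stereotactic or small field brain irradiation must have completed at least 2 weeks prior to study entry" and "Whole brain radiation must have completed at least 4 weeks prior to study entry". Palliative radiation of up to 10 fractions "must have been completed at least 48 hours" before entry.

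**Age and choice of the baseline scan.** In the Schedule of Activities, screening items are "to be obtained within 28 days prior to registration", and "Registration will be within 2 days prior to study treatment start". Under Protocol Section 8, routine procedures "obtained before signing of the ICF may be utilized for screening or baseline purposes" if they meet the protocol criteria and time frame. SAP 5.2.8 requires that "All baseline assessments must be within 28 days prior to and including the date of first dose". SAP 3.4 takes the last tumor assessment before treatment start as baseline. None of these provisions orders the scan relative to radiotherapy.

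**Rules that touch on local treatment.** Appendix 5 says that "Tumor lesions situated in a previously irradiated area" are usually not measurable unless they have progressed. SAP 6.1.1 drops response data obtained after subsequent anti-cancer therapy. SAP 6.2.2 says that surgery or radiotherapy to extracranial lesions leaves intracranial response unaffected. SAP 6.5.1 tabulates prior radiotherapy. The subset analyses in SAP 6.4 do not use it.

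**The concern.** Response is measured against the baseline scan. If a lesion is scanned, then irradiated, then followed on lorlatinib, the change from baseline mixes the two treatments. In a single-arm study no control group carries the same mixture, and for response the error runs in favour of lorlatinib.

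The Appendix 5 rule does not catch this sequence. On the baseline scan the lesion had not yet been irradiated, so a reader could properly choose it as a target. The SAP exclusion does not catch it either, because the radiotherapy comes before the first dose and is not subsequent therapy.

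At stake is the intracranial response rate, which the primary objective names beside the overall rate. To a lesser degree the overall rate is affected too.

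**Working it through.** **1. The plan's own figures.** The exact lower limit for x responders of n is the 2.5% quantile of a Beta(x, n − x + 1) distribution.
- 26/60 = 43.3% gives a lower limit of 30.6%, and 25/60 gives 29.1%. The sample-size statement in Protocol 9.2 is reproduced.
- 60/0.85 = 70.6, against the stated 70.
- At n = 70, 30 responders (42.9%) give 31.1% and pass; 29 give 29.8% and fail.

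**2. The window.** Largest gap from scan to end of radiotherapy = 28 days − required interval before entry.

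| Radiotherapy | Interval before entry | Largest gap after scan |
|---|---|---|
| Brain stereotactic or small-field | 14 days | 28 − 14 = 14 days |
| Other non-palliative | 14 days | 28 − 14 = 14 days |
| Palliative, bone pain | 2 days | 28 − 2 = 26 days |
| Whole brain | 28 days | 28 − 28 = 0 days |

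The protocol counts the 28 days from registration and the SAP from first dose, and study entry is not tied to either. With a scan 28 days before registration, registration 2 days before dosing and entry read as first dose, the gaps would be 16, 16, 28 and 2 days. That scan would be 30 days before dosing and would fail SAP 5.2.8, so 14 and 26 days are the relevant limits.

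**3. An example.** A brain lesion is seen on MRI at day −26 and stereotactic treatment ends at day −16, with entry and first dose on day 0. The scan is inside 28 days and the treatment is outside 14. The first two scheduled scans, at weeks 6 and 12, are far enough apart to give a confirmed response.

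**4. Intracranial response.** Only brain lesions are assessed, so one irradiated lesion can be the whole target sum. For a single 12 mm target, a partial response needs a fall of 0.30 × 12 = 3.6 mm. The analysis set (SAP Section 4) takes anyone with a brain lesion at entry, measurable or not. A non-target lesion that disappears could therefore count as a complete response, which measurability rules do not prevent.

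One response moves the rate by 100/n points. The documents do not give n:
- n = 20: 5.0 points
- n = 30: 3.3 points
- n = 40: 2.5 points

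**5. Overall response.** Inclusion 4 requires a measurable extracranial target, and a partial response needs a 30% fall in the whole target sum. Take a 12 mm irradiated brain target and let the other targets total T mm, unchanged.
- With T = 10, the sum is 22 mm and the required fall is 6.6 mm, or 6.6/12 = 55% of the brain lesion.
- If the lesion becomes too small to measure (5 mm imputed, SAP 5.2.7), the fall is 7 mm. That suffices only if 7/(12 + T) ≥ 0.30, so T ≤ 11.3 mm.
- If it disappears, 12/(12 + T) ≥ 0.30 requires T ≤ 28 mm.

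If the other targets are shrinking but fall short of 30%, a smaller contribution would be enough. For bone, only lytic or mixed lesions with a measurable soft-tissue part can be targets (Appendix 5). Under Appendix 5 Table 5, irradiating a non-target lesion cannot by itself turn stable target disease into an overall response.

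**The case against.** The strongest objection concerns impact. A reader might infer that one such response can reverse the primary conclusion, since 30/70 passes and 29/70 fails. The arithmetic is right, but it holds for any single misclassified response at that boundary and does not measure this bias. The route to an overall response is narrow, as step 5 shows. A reader might also treat intracranial response as co-primary because the primary objective names it. It is listed as a secondary endpoint (Protocol Section 3 and 9.4.1), and the decision rule (SAP 5.1.2) concerns the overall rate alone. Both points stand.

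Frequency is also unknown. Nothing in the documents says how many participants would be irradiated between scan and dosing, and eligible CNS metastases must be asymptomatic, including those controlled on stable or decreasing steroids. This stands, so no total bias can be stated.

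The remaining safeguards are partial:
- Inclusion 4 describes brain metastases as newly diagnosed or as progressive after local treatment. A lesion just irradiated and not progressed fits only a permissive reading of the first alternative. The text does not exclude it, and this does not touch extracranial lesions.
- SAP 5.2.6 lets the independent oncologist use additional clinical information, but SAP 6.1.1 derives best response from the radiologist's timepoint reads.
- Exclusion 1 bars anti-cancer treatment other than first-line alectinib or ceritinib, and SAP 6.5.1 counts radiation as anti-cancer treatment. Read literally, this conflicts with criterion 11, which plainly expects prior radiotherapy. The passages must be reconciled, but they do not close the gap.

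**Conclusion.** The concern holds as a gap in the response rules. Radiotherapy may end up to 14 days (brain stereotactic, small-field or other non-palliative) or 26 days (palliative bone) after the scan used as baseline, and nothing stops the resulting shrinkage from counting. Whole-brain radiotherapy is effectively closed off by its 4-week interval.

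The consequence is an upward error mainly in the intracranial response rate, a descriptive secondary estimate. It is 2.5 to 5.0 points per affected participant for assumed subsets of 40 down to 20. For the overall response rate the effect is possible but requires the irradiated lesion to be a target that makes up much of the target sum. The documents do not support a claim that the primary conclusion is in specific danger from this source. The windows are certain from the text; the size of the bias is not, because its frequency is not given. A change is worth making because the error runs one way and the remedy is cheap.

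**What to change.** In SAP 6.1.1 and 6.2.2, for both central and investigator assessment, add a lesion-level rule. A lesion given radiotherapy or another local procedure between the scan used as baseline and first dose is not used as a target, and its shrinkage or disappearance does not count toward overall or intracranial response. Growth of that lesion and new lesions still count as progression.

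Add a sensitivity analysis that counts participants whose response depends on such a lesion as non-responders, for both rates. It should largely agree with the main analysis where the lesion rule is fully applied, and it protects the result where images were read without the radiotherapy record.

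Do not put the rule in SAP 5.2.8. A criterion there would make the participant's whole baseline inadequate. That forces non-response (SAP 3.1.1) and censors PFS and TTP at first dose, apart from the early-death provision (SAP 6.2.7 and 6.2.8), even for one palliated non-target bone lesion. Baseline adequacy, including measurability as read on the baseline scan, and PFS and TTP censoring should stay unchanged. The radiotherapy washouts also stay as written. No repeat scan is needed, and one would not remove shrinkage that continues after it.

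The cost is a short SAP addition and a slightly lower intracranial response rate. The documents show that prior radiotherapy is tabulated, but not that site and dates can be linked to each lesion. The sponsor must confirm this and give the information to the central readers.

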### **Other Exclusions**

- 15. Known prior or suspected severe hypersensitivity to study interventions or any component in their formulations.
- 16. Investigator site staff members directly involved in the conduct of the study and their family members, site staff members otherwise supervised by the investigator, or Pfizer employees, including their family members, directly involved in the conduct of the study.

## 5.3. Lifestyle Considerations

1. See Appendix 4 for mandatory contraception information.

- 2. Refrain from consumption of grapefruit/grapefruit related citrus fruits (eg, Seville oranges pomelos) from 1 day before the start of study intervention until after the final dose.
- 3. Lorlatinib has moderate influence on the ability to drive and use machines. Cautions should be exercised when driving or operating machines as participants may experience CNS effects.

#### 5.4. Screen Failures

Screen failures are defined as participants who consent to participate in the clinical study but are not subsequently entered in the study. A minimal set of screen failure information is required to ensure transparent reporting of screen failure participants to meet the Consolidated Standards of Reporting Trials (CONSORT) publishing requirements and to respond to queries from regulatory authorities. Minimal information includes demography, screen failure details, eligibility criteria, and any serious adverse event (SAE).

Individuals who do not meet the criteria for participation in this study (screen failure) may not be rescreened.

#### 6. STUDY INTERVENTION

Study intervention is defined as any investigational intervention(s), marketed product(s), placebo, or medical device(s) intended to be administered to a study participant according to the study protocol.

## 6.1. Study Intervention(s) Administered

ARM Name	Lorlatinib 100 mg QD
Intervention Name	lorlatinib
Туре	Small molecule
Dosage Form	Tablet
Dose Strength	25 mg
Dosage	100 mg QD
Route of Administration	Oral
Sourcing	Provided centrally by the Sponsor
Packaging and Labeling	Study Intervention will be provided in bottles. Each bottle
	will be labeled as required per country requirement.
Current/Former Name(s)	PF-06463922/lorlatinib
or Alias(es)	

## 6.2. Preparation/Handling/Storage/Accountability

1. The investigator or designee must confirm appropriate temperature conditions have been maintained during transit for all study intervention received and any discrepancies are reported and resolved before use of the study intervention.

- 2. Only participants enrolled in the study may receive study intervention and only authorized site staff may supply or administer study intervention. All study intervention must be stored in a secure, environmentally controlled, and monitored (manual or automated) area in accordance with the labeled storage conditions with access limited to the investigator and authorized site staff. At a minimum, daily minimum and maximum temperatures for all site storage locations must be documented and available upon request. Data for nonworking days must indicate the minimum and maximum temperature since previously documented for all site storage locations upon return to business.
- 3. The investigator, institution, or the head of the medical institution (where applicable) is responsible for study intervention accountability, reconciliation, and record maintenance (ie, receipt, reconciliation, and final disposition records). All study interventions will be accounted for using an investigational product accountability form/record.
- 4. Further guidance and information for the final disposition of unused study interventions are provided in the investigational product (IP) manual.
- 5. Any storage conditions stated in the SRSD will be superseded by the storage conditions stated on the product label.
- 6. Study interventions should be stored in their original containers and in accordance with the labels.
- 7. Site staff will instruct participants on the proper storage requirements for take-home study intervention.
- 8. Deviations from the storage requirements, including any actions taken, must be documented and reported to Pfizer upon discovery. The site should actively pursue options for returning the study intervention to the storage conditions described in the labeling, as soon as possible. Once an excursion is identified, the study intervention must be quarantined and not used until Pfizer provides permission to use the study intervention. It will not be considered a protocol deviation if Pfizer approves the use of the study intervention after the temperature excursion. Use of the study intervention prior to Pfizer approval will be considered a protocol deviation. Specific details regarding the definition of an excursion and information the site should report for each excursion will be provided to the site in the IP manual.
- 9. The sponsor or designee will provide guidance on the destruction of unused study intervention (eg, at the site). If destruction is authorized to take place at the investigator site, the investigator must ensure that the materials are destroyed in compliance with applicable environmental regulations, institutional policy, and any special instructions provided by Pfizer, and all destruction must be adequately documented.

